General anesthetic and sedative agents induce highly structured oscillations in the EEG.^{iv} There is growing evidence that these oscillations relate directly to the systems-level mechanisms by which anesthetics produce altered states of consciousness. During normal brain function, oscillations regulate the timing and coordination of brain activity within and between functional systems and circuits. Anesthesia induced oscillations are thought to disrupt this coordinated activity, producing different states of altered arousal depending upon the receptors and circuits upon which the drugs act.^v General anesthesia with sevoflurane is characterized in the EEG by frontally coherent alpha (8–12 Hz), delta (1–4 Hz), and high amplitude slow (0.1–1Hz) oscillations.^{vi} This pattern, observed when adult patients are sufficiently anaesthetized to conduct surgery, is similar to that observed under propofol-induced general anesthesia and suggests a common systems-level mechanism of action.^{vii} Given that the brain rapidly develops and undergoes significant changes from

childbirth into adulthood, anesthesia induced EEG oscillations in children might differ from those of adults, and could vary significantly with age. Characterizing the structure of the EEG in relation to age would help establish the foundations for age-appropriate monitoring of brain states during general anesthesia and sedation in children. We aimed to examine the effects of age on the EEG during general anesthesia, with sevoflurane as the sole hypnotic agent. The EEG is typically described in terms of rhythmic activity and transients. The rhythmic activity is divided into bands by frequency (figure 1 and figure 3).

Objective

Aim:

This study is designed to evaluate the correlation of raw EEG patterns and age under 1.0 MAC sevoflurane.

Study design and purpose

This study is being conducted to evaluate and assess the electroencephalography wave patterns in different age patients undergoing surgery under general anesthesia. The aim of our study is to compare the raw EEG waves in different age patients and analyze any changes in these patterns among various age groups and which of these groups will have the EEG signal of high-frequency waves or low frequency waves. Previous studies have shown that light sedation is often accompanied by decreasing posterior alpha waves and increasing the intensity of frontal/central beta waves.

Sample size: 120

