Based on 6 different age groups from infants to elderly (0-80 years old), we are recruiting 120 patients with an American Society of Anesthesiology score (ASA) I or II, scheduled for elective surgery under general anesthesia lasting less than 2 hours. Each group will have 20 cases.

Methods:

A sample of 120 healthy patients from the Second Affiliated Hospital of Wenzhou Medical University with American Society of Anesthesiologists (ASA) physical status I or II will be randomly selected and included in this study. After obtaining ethical approval and written informed consent, we will enroll 120 patients (ASA I and II), aged 0-80 years of either gender undergoing minor elective surgery. The selected patients will be divided into 6 different groups according to their age (figure 2). The surgeries will last less than two hours each and will be performed under general anesthesia which is an indispensable part of surgery. Depth of anesthesia and electrical brain activity will be monitored using Bispectral index monitoring system. However, these are based on the underlying changes in the features of an EEG signal as the signals vary with the level of anesthesia. We will compare the different EEG waves (alpha, delta, theta and gamma) for all age patients while maintaining 1.0 MAC sevoflurane. Data related to non-invasive blood pressure, heart rate, respiration rate, oxygen saturation, EEG waves frequencies, end tidal volume of sevoflurane and BIS values will be recorded. These data will be analyzed every 1 min for the first 10mins during maintenance of anesthesia with 1.0 MAC sevoflurane. Data collection will be first recorded after tracheal intubation. The raw EEG wave will be recorded by means of a Universal Serial Bus (USB) which will later be analyzed and processed offline.

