All patients will be ventilated using an Ohmeda-Datex anesthetic machine with soda lime (CO₂ absorber). Hypotension, defined as a decrease in blood pressure by 25% from baseline, will be treated with intravenous fluid or phenyl ephedrine (20 microgram bolus). Raw EEG data, BIS values and end target expiratory concentration of sevoflurane will be recorded every one minute for a period of 10 mins after induction and intubation. Raw EEG data (figure4-patient of 80 years old), will be analyzed and processed using the pdf screenshot from the BIS vista monitor. The pdf screenshots of the raw EEG will be recorded by means of a Universal Serial Bus (USB). The pdf screenshots will be taken twice during the 10 minutes of recording to minimize any loss of data.

Inclusion Criteria:

Patients age between 0 to 80 years old, ASA I or II scheduled for minor surgeries under general anesthesia lasting less than 2 hours each.

Exclusion Criteria:

Potential subjects with any neurologic or psychiatric disease, relative or absolute contraindication to sevoflurane including pregnancy by patient self-report, and any recent

prescription or illicit medication use will be excluded. Patients with a history of any disabling central nervous or cerebrovascular disease and patients who had received central nervous system-active drugs will be excluded from the study. We will exclude patients with poor quality data, most likely because of poor electrode contact.

Potential benefits

The advantages of this study are to help the anesthesiologist have a better understanding of the brain waves under general anesthesia. EEG monitoring provides assessment of brain perfusion during state of general anesthesia. Brain death during anesthesia can be assessed and prevented with the use of raw EEG patterns.

EEG waves monitoring is a key aspect in preventing brain damage and ensuring the level of anesthesia is within the required range.

Maintaining the required range of deep anesthesia (BIS value of 40 to 60) helps avoid the incidence of awareness with recall in adults during general anesthesia and sedation.

Potential risks

There are no risks and complications associated with this study. However, mild redness may appear on the forehead in some patients from the BIS electrodes.

Statistics:

Statistical analyses will be performed with a statistical package (SPSS version 21.0; SPSS, Chicago, IL) and Microsoft excel. All data will be presented as mean \pm sd.

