**STATISTICAL PLAN:**

Statistical analyses will be performed with a statistical package (SPSS version 21.0; SPSS, Chicago, IL) and Microsoft excel. All data will be presented as mean  $\pm$  sd. Demographic data will be compared by using standard t-tests; comparison of incidence data between groups performed by using Fisher's exact tests. A P value  $< 0.05$  will be considered significant.

Data related to non-invasive blood pressure, heart rate, respiration rate, oxygen saturation, EEG waves frequencies, end tidal volume of sevoflurane and BIS values will be recorded. These data will be analyzed every 1min for the first 10mins during maintenance of anesthesia with 1.0 MAC sevoflurane. Data collection will be first recorded after tracheal intubation. The raw EEG wave will be recorded by means of a Universal Serial Bus (USB) which will later be analyzed and processed offline.

EEG waves , BIS values and Et sevoflurane will be collected every 1minute for a period of 10 minutes at T1,T2,T3,T4,T5,T6,T7,T8,T9,T10.

Non-invasive blood pressure, heart rate, respiration rate and oxygen saturation values will be recorded every 3 minutes for the same period (10minutes).

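### The only EEG variable listed for analysis is wave frequency, with no amplitude or power measure, so the plan cannot show how the balance of EEG components changes with age

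*Protocol*

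**What the plan says.** - **Purpose.** The protocol's section on study design and purpose wants to compare raw EEG between age groups and to learn "which of these groups will have the EEG signal of high-frequency waves or low frequency waves". It gives no cut-off between high and low.
- **Comparison.** Methods states: "We will compare the different EEG waves (alpha, delta, theta and gamma) for all age patients".
- **Variables.** The data list in the SAP, which matches the one in the protocol's Methods, reads: "EEG waves frequencies, end tidal volume of sevoflurane and BIS values will be recorded". It gives no unit for the frequency and no rule for deriving it. Neither amplitude nor power is listed.
- **Summary.** The protocol's Statistics section and the SAP both state "All data will be presented as mean" ± SD. They name t-tests for demographic data and Fisher's exact tests for incidence data, and assign no test to the EEG.
- **Expected signal.** The Background describes the EEG of anesthetised adults as "frontally coherent alpha (8–12 Hz), delta (1–4 Hz), and high amplitude slow (0.1–1Hz) oscillations". It adds that children's oscillations might differ and could vary strongly with age.
- **Bands.** Figure 1 sets delta below 4 Hz, theta from 4 to below 8, alpha from 8 to below 14, and beta from 14 upward. It has no gamma band and no separate slow band.
- **Capture.** Methods describes a continuous 10-minute recording, with the raw wave stored on USB for offline processing. The SAP says "EEG waves , BIS values and Et sevoflurane will be collected every 1minute for a period of 10 minutes", at T1 to T10. A later paragraph of Methods says that the raw EEG will be analysed from PDF screenshots of the monitor, taken twice in the 10 minutes.

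**The concern.** By the protocol's own account, the adult sevoflurane EEG contains low- and high-frequency activity at the same moment. What may change with age is how much of each is present. That is a question about strength, and the protocol itself writes in those terms: it calls the slow component high in amplitude and describes light sedation by the intensity of beta activity. The listed outcome records only frequency.

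At stake is the trial's central comparison. Two age groups could have different mixtures and the same mean frequency. A fall in alpha power at unchanged alpha frequency would leave the mean frequency within the alpha band untouched. The report could then describe such groups as alike, or describe a difference without showing which component produced it.

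**Working it through.** **The plan's own figure.** The only design figure that can be reproduced is the sample size: 6 groups × 20 = 120, as stated. The documents give no expected EEG frequency, power, SD or effect size.

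**Inputs.** The component ranges come from the Background, and I take their midpoints: slow (0.1 + 1)/2 = 0.55 Hz; delta (1 + 4)/2 = 2.5 Hz; alpha (8 + 12)/2 = 10 Hz. Band labels follow Figure 1. The component shares *w* are my assumptions, so several are shown.

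**Formula.** Mean frequency = 0.55·w(slow) + 2.5·w(delta) + 10·w(alpha), with shares adding to 1.

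**Step 1: can different signals share one mean?** For delta plus alpha only, 2.5 + 7.5·w(alpha) = 6 gives w(alpha) = 3.5/7.5 = 0.467. So 53% delta and 47% alpha average 6.0 Hz, as does a pure 6 Hz theta signal.

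**Step 2: where does the mean fall?**

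| Slow / delta / alpha shares | Mean (Hz) | Figure 1 band |
|---|---|---|
| 0.6 / 0.3 / 0.1 | 0.33 + 0.75 + 1.0 = 2.08 | delta |
| 0.5 / 0.3 / 0.2 | 0.275 + 0.75 + 2.0 = 3.025 | delta |
| 0.4 / 0.3 / 0.3 | 0.22 + 0.75 + 3.0 = 3.97 | delta |
| equal thirds | 13.05/3 = 4.35 | theta |
| 0.25 / 0.25 / 0.5 | 0.1375 + 0.625 + 5.0 = 5.76 | theta |
| 0.05 / 0.15 / 0.8 | 0.0275 + 0.375 + 8.0 = 8.40 | alpha |

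With equal thirds, using the lower and then the upper range limits instead of midpoints gives 9.1/3 = 3.03 Hz to 17/3 = 5.67 Hz.

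The alpha shares for which the mean lies in theta (4 to below 8 Hz) depend on what makes up the rest:
- delta only: (4 − 2.5)/7.5 = 0.20 to (8 − 2.5)/7.5 = 0.733;
- slow only: (4 − 0.55)/9.45 = 0.365 to (8 − 0.55)/9.45 = 0.788;
- slow and delta equally (mean 1.525): 2.475/8.475 = 0.292 to 6.475/8.475 = 0.764.

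**Step 3: does another reading of frequency avoid the problem?** Compare the second and first rows of the table, where the alpha share halves from 0.2 to 0.1.
- *Mean frequency within each band:* alpha is 10 Hz in both, so no change is seen.
- *Dominant band each minute:* activity below 4 Hz makes up 0.8 and then 0.9, so the label is delta in both.
- *Pooled mean frequency:* it moves from 3.025 to 2.08 Hz and stays in delta. A single number cannot show that less alpha, rather than slower delta or more slow activity, is the cause.

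None of the three readings recovers the balance of components.

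**The case against.** The strongest reply is that the documents do not choose a wrong measure; they leave the measure undefined. Methods plans a comparison by named wave types, Figure 1 defines bands, and mean ± SD could be applied band by band. The raw waveform is to be recorded, and a waveform carries amplitude. The Fisher tests for incidence data also show that the rule about means is not meant literally for everything.

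Much of this stands, and it rules out several readings that a reader might infer:
- *That one pooled mean frequency per patient is planned.* The documents do not say so, and the band comparison in Methods points away from it.
- *That the mean falls in theta.* This depends on shares that the documents do not give. Since the slow component is described as high in amplitude, a power-weighted mean could well lie in delta.
- *That a dominant-band label gives the same false theta.* It does not: an alpha-delta mixture would be labelled alpha or delta. It loses graded change in the other components instead.
- *That patients will be sorted into high- and low-frequency classes.* The purpose section asks a question and sets no such rule.
- *That the three-component pattern holds at every age.* It is described for adults only.

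The reply does not supply the missing measure. Planning to compare waves and storing a waveform do not define an outcome, and the one quantity listed is frequency, which fails under each reading in Step 3.

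**Conclusion.** The point holds in this form: the EEG outcome is given only as frequency, summarised as mean ± SD, and no amplitude or power measure is defined for the band comparison that Methods promises. Such an outcome cannot show how the balance of slow, delta, theta and alpha activity changes with age. The 6.0 Hz example shows that masking can occur; it does not estimate how often it will. It rests on band midpoints and assumed shares. The qualitative conclusion does not depend on those shares, because a mean that lands in delta hides alpha just as one in theta does. That children may differ from adults strengthens the case for a measure able to show the difference.

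It would go too far to say that the study cannot answer its question. If the digital waveform is kept, band power can be computed from it. This is a worthwhile and fairly cheap improvement to the central outcome, provided that the signal is captured in usable form.

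**What to change.** 1. Replace frequency as the EEG outcome, in the protocol and the SAP, with power in each defined band for each patient and each of T1 to T10: log absolute power and share of total power.
2. Name one band measure in advance as the main outcome, say how the ten time points are combined, and present it by age group with the other bands alongside. The choice of band is the investigators'.
3. Reword the high/low-frequency purpose as band power by age.
4. Settle the bands. Methods lists gamma but not beta; Figure 1 lists beta but not gamma. Figure 3, also cited for the bands, could not be seen and may bear on this. Say whether slow activity is separate from delta, and whether alpha ends at 12 Hz (Background) or 14 Hz (Figure 1).
5. Reconcile the two accounts of capture. Continuous raw EEG with ten time points and analysis of PDF screenshots taken twice cannot both be the data source. Band power should come from the digital signal; confirm that the monitor in use can export it.

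The cost is revised wording and a standard spectral calculation on a recording that Methods already intends to process offline. It rises if only screenshots were to be stored, since power may not be recoverable from them, so item 5 is best settled before recordings are made. The results will also contain several band measures instead of one number, which is why one must be named as the main outcome.

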**STATISTICAL PLAN:**

Statistical analyses will be performed with a statistical package (SPSS version 21.0; SPSS, Chicago, IL) and Microsoft excel. All data will be presented as mean  $\pm$  sd. Demographic data will be compared by using standard t-tests; comparison of incidence data between groups performed by using Fisher's exact tests. A P value  $< 0.05$  will be considered significant.

Data related to non-invasive blood pressure, heart rate, respiration rate, oxygen saturation, EEG waves frequencies, end tidal volume of sevoflurane and BIS values will be recorded. These data will be analyzed every 1min for the first 10mins during maintenance of anesthesia with 1.0 MAC sevoflurane. Data collection will be first recorded after tracheal intubation. The raw EEG wave will be recorded by means of a Universal Serial Bus (USB) which will later be analyzed and processed offline.

EEG waves , BIS values and Et sevoflurane will be collected every 1minute for a period of 10 minutes at T1,T2,T3,T4,T5,T6,T7,T8,T9,T10.

Non-invasive blood pressure, heart rate, respiration rate and oxygen saturation values will be recorded every 3 minutes for the same period (10minutes).
